This cross-over study aims to investigate the impact of two metabolically distinct diets on Glycated hemoglobin, cardiovascular health, the gut microbiome, and metabolic status. Participants are recruited using media advertisements, email lists, and clinician referral ([name]) from previous recruitment for nutrition studies conducted by our laboratory group. Forty participants are planned to be randomized between the two arms: (1) start with 12 week WFKD and switch to 12 week Med-Plus; (2) start with 12 week Med-Plus and switch to 12 week WFKD. Randomization will be stratified by diabetes vs pre-diabetes status. As displayed in figure above, clinical and metabolic measurements are taken at baseline, and weeks 0, 6, 12, (Phase I, weeks 1-12), 18, 24 (Phase II, weeks 13-24) and 36 (Maintenance Phase). Continuous glucose monitoring will be collected five times during the trial, each time data will be collected every hour for ten days.

Primary Outcome:

• Difference in percent difference from baseline after 12 weeks of each phase

Secondary Outcomes:

- Difference in percent difference from baseline in LDL cholesterol after 12 weeks of each phase
- Difference in percent difference from baseline in HDL cholesterol after 12 weeks of each phase
- Difference in percent difference from baseline in triglycerides after 12 weeks of each phase
- Difference in percent difference from baseline in fasting insulin after 12 weeks of each phase
- Difference in percent difference from baseline in blood pressure after 12 weeks of each phase
- Difference in percent difference from baseline in weight after 12 weeks of each phase
- Difference in percent difference from baseline in alpha diversity after 12 weeks of each phase. Primary metric of alpha diversity will be using number of observed sequence variants ("species") determined by standard 16S rRNA amplicon sequencing (V3-V5 region followed by DADA2 to define error-corrected sequence variants). *Note: Higher alpha diversity is better. The units are the # of sequence variants*
- Difference in percent difference from baseline in composite of short-chain fatty acids (SCFA) concentration (ug/g stool: acetate + propionate + butyrate) after 12 weeks of each phase

Exploratory outcomes:

- Difference in satisfaction with WFKD and Med-Plus diets, using a 5-point Likert scale (1=not at all satisfied; 2=slightly satisfied; 3=moderately satisfied; 4=very satisfied; 5=extremely satisfied).

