- Difference in adherence to diet protocols by diabetes vs. pre-diabetes status, according to 3day food records.
- Tabulate COVID-19 Survey answers

Primary Analysis

Patient demographics and baseline clinical characteristics will be summarized by arm, as n (%) and median (interquartile range) for categorical and continuous variables, respectively. To assess any differences in each variable between the two arms, the absolute standardized differences are presented, where a value of 0.2 or less, 0.5, and 0.8 or more correspond to small, medium, and large differences, respectively. Characteristics found to display large differences will be adjusted for in a sensitivity analysis. We will also compare rate of adherence for WFKD after 12 weeks and Med-Plus diets after 12 weeks using a Fisher's Exact test with weekly NDSR (and Cronometer) data. We will develop a composite score to measure a participant's adherence to each diet.

We will use a mixed-effects linear model (1) with HbA1c percent difference from baseline for diet, j, as the outcome. We want to assess for a difference in diet (WFKD vs Med-Plus), while adjusting for fixed effects: order (e.g. study arm), pre-diabetes vs. diabetes status, and a random effect for each participant, i.

$$\left(\frac{HbA1c_{ij}-HbA1c_{i0}}{HbA1c_{i0}}\right) = \beta_o + \beta_1 Order_i + \beta_2 Diabetes_i + \beta_3 Diet_{ij} + \gamma_i$$
(1)

For the primary outcome, we will use a two-sided likelihood ratio test to test for no difference between diet types. The primary analysis will include participants with baseline blood draws, and at least one blood draw in each phase (including crossing over). The primary analysis will be a complete case analysis and use participants' last available lab values in each phase or week 12, if available; patients who did not complete both phases (i.e. crossover) will be excluded. A significance level of 0.05 is set for all analyses. In a sensitivity analysis, we will adjust for baseline weight and percent weight change if weight change from baseline is found to be significant, since this is known to impact HbA1c values; and in a separate analysis, we will adjust for adherence to each diet.

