Similarly, for our secondary outcomes, we will use separate mixed-effects models to evaluate fasting lipids, insulin, glucose, blood pressure and short-chain fatty acids for WFKD vs Med-Plus, adjusting for order, phase, pre-diabetes vs. diabetes status, and repeated measures. A two-sided likelihood ratio test will be used to assess no difference between diet types. For our exploratory outcome comparing diet satisfaction, we will use a Wilcoxon signed-rank test to evaluate the null hypothesis that the difference between pairs follows a symmetric distribution around zero, which indicates similar satisfaction with both diets. We will use a Fisher's Exact test to evaluate any difference in the rate of adherence due to diabetes vs pre-diabetes status, within each diet.

Sensitivity Analysis

Due to COVID-19, visits to collect blood draws were delayed for some participants. These participants report they maintained the phase's diet until the lab measurements could be collected. We will check adherence to diet based on NDSR at Week 12 and Week 12 extra visit (taken when allowed back into clinic), and also check for a change in dietary and exercise habits during shelter-in-place. Potential impact of delays are unclear; subsequently, we will perform a number of sensitivity analyses:

Sensitivity Analysis 1 (SA1): For a simple truncated analysis, we will consider only the first phase (12 weeks) of each group and compare differences (two-sample)

Sensitivity Analysis 2 (SA2): For a simple estimate of Week 12 analysis, we will consider the average of the last lab measurement of each 12 week phase and the extra data point at Week 12 extra visit.

Sensitivity Analysis 3 (SA3): For an extended-phase analysis, we will consider using the last lab measurement from each phase, i.e. the "extra" data timepoints after week 12 in study for some participants.

Sensitivity Analysis 4 (SA4): For a pre-COVID-19 truncated analysis, we will consider the subset of data prior to the official Shelter-in-Place date for the Bay Area, March 16, 2020.

Sensitivity Analysis 5 (SA5): To assess any effect on outcomes due to COVID-19 impact on logistics, we will consider the subset of data when participants received groceries for each diet. We will also evaluate if adherence was better for the first four weeks when groceries were delivered.

Secondary Analysis

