For our secondary analysis, we want to investigate: (a) a potential difference in the primary outcome by diabetes status; (b) the different trajectories of each diet; and (c) different metrics using continuous glucose monitoring data and how that compares with the gold standard HbA1c data. In a low-power analysis for (a), we will use model (1) and include an interaction term for diet and diabetes status. For (b), we will use all time points in a model similar to (1) but with a time variable. Lastly for our analysis in (c), we will consider different metrics used in the literature for continuous glucose monitoring and compare trajectories of each metric with that of the gold standard using HbA1c data.

Exploratory Analysis

For our exploratory analysis, we want to investigate long term maintenance. Upon completing both diet phases, for three months participants were instructed to eat the diet of their choosing. This analysis will be largely descriptive on what participants were consuming and their change in lab measurements.

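### The primary HbA1c model has no phase term, although the secondary models do, so a shift between Phase I and Phase II would cost power or bias the diet estimate

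*SAP*

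**What the plan says.** The Study Design section describes a two-sequence, two-period crossover. "Forty participants are planned to be randomized between the two arms", one starting on each diet, with Phase II following directly on Phase I. The SAP gives no allocation ratio, dropout rate, SD or power calculation.

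Under Primary Analysis, the HbA1c percent difference from baseline is modelled for each diet "while adjusting for fixed effects: order (e.g. study arm), pre-diabetes vs. diabetes status, and a random effect for each participant, i". Equation (1) matches the text: Order, Diabetes, Diet and a participant effect. Diet is tested by a two-sided likelihood ratio test (LRT) at 0.05. The set is complete cases: "patients who did not complete both phases (i.e. crossover) will be excluded".

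The secondary outcomes are introduced as being handled in a similar way, but their models are specified as "adjusting for order, phase, pre-diabetes vs. diabetes status, and repeated measures". In Secondary Analysis, item (a) reuses the primary model: "we will use model (1) and include an interaction term for diet and diabetes status".

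**The concern.** The SAP treats order and phase as two separate terms, and leaves phase out of the primary model only. Order is glossed as study arm and indexed by participant, so it cannot be read as phase under another name. In a 2x2 crossover, phase corresponds to the Order-by-Diet interaction, which model (1) does not contain.

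A shift between phases is plausible on the SAP's own account, though not established. Both phases are measured against one baseline, so any time trend in HbA1c appears as a phase difference. Visits were disrupted by COVID-19, of which the SAP says "Potential impact of delays are unclear; subsequently, we will perform a number of sensitivity analyses".

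At stake is the primary test. An unmodelled shift either inflates the residual and lowers power or, when the completer arms differ in size, also moves the diet estimate.

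**Working it through.** **No figure to reproduce.** The SAP has no power calculation behind its 40 participants, so what follows shows the size of the effect under stated assumptions.

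**Inputs from the SAP:** 40 participants planned; two-sided LRT at 0.05; complete pairs only.

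**Assumed:** the SD of the within-person difference is 1 (all effects are in this unit). The Phase II minus Phase I shift *p* is 0.25, 0.5 or 1.0. The diet effect *d* is 0.455, which gives 80% power for a phase-adjusted t test at N = 40. Completer splits are 20/20, or 18/15, 19/14 and 20/13 (N = 33).

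**Step 1: what model (1) estimates.** Let D be WFKD minus Med-Plus within a person, with n1 WFKD-first completers, n2 Med-Plus-first completers and N = n1 + n2. Order and Diabetes do not vary within a person, so with complete pairs and a non-zero participant variance the diet estimate is the mean of D. The LRT statistic is N × ln(RSS0/RSS1) computed on D. Maximum-likelihood mixed models fitted to 90 simulated data sets agreed with both statements to rounding error.

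**Step 2: effect of a shift.** E[D] = d − p in WFKD-first participants and d + p in Med-Plus-first participants. Therefore:

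- without phase, bias = p(n2 − n1)/N;
- without phase, the variance behind the SE is about 1 + 4p²·n1·n2/N²;
- with phase, the estimate is the unweighted average of the two arm means: bias 0, residual variance 1, and an SE larger by 1/√(1 − r²), where r = (n1 − n2)/N.

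**Step 3: equal arms, 20/20.** Bias is 0 and the SE multiplier is √(1 + p²).

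| p | SE multiplier | LRT power without phase | with phase | LRT type I error without phase | with phase |
|---|---|---|---|---|---|
| 0.25 | √1.0625 = 1.03 | 79.4% | 81.8% | 4.8% | 5.8% |
| 0.5 | √1.25 = 1.12 | 74.1% | 81.8% | 3.2% | 5.8% |
| 1.0 | √2 = 1.41 | 52.6% | 81.8% | 0.7% | 5.8% |

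**Step 4: unequal arms.**

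| Split | Bias / p | Absolute bias at p = 0.5 | Share of d = 0.455 | SE factor if phase is added |
|---|---|---|---|---|
| 18/15 | 3/33 = 9% | 0.045 | 10% | 1.004 |
| 19/14 | 5/33 = 15% | 0.076 | 17% | 1.012 |
| 20/13 | 7/33 = 21% | 0.106 | 23% | 1.023 |

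At 20/13 and p = 0.5, LRT power without phase is 42% when the bias opposes the true effect and 84% when it adds to it, against 72% with phase. The 84% is not a gain, because the estimate is biased away from zero. At 18/15 in the unfavourable direction, power is about 56% against 74%.

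**Step 5: type I error.** At 20/13 and p = 1.0 it is 6.7% without phase and 6.0% with it. At 18/15 the test is conservative (3.9% at p = 0.5). Inflation needs strong imbalance: at 20/11 about 9.2% at p = 0.5 and 13.8% at p = 1.0.

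Power and type I error in the tables come from numerical integration over the noncentral chi-square distributions; simulation of 100,000 trials per cell agrees to within about half a percentage point.

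**The case against.** The strongest reply is that the harm depends on a shift the SAP does not demonstrate. Delayed blood draws affected only some participants, who reported keeping to their diet meanwhile. That is not evidence of a shift common to everyone, and a phase term removes only the average shift. At p = 0.25 with equal arms the loss is 2.4 power points. The 1.0 SD case assumes a shift more than twice the assumed diet effect. Large type I inflation needs losses almost entirely in one arm. With equal arms model (1) is an unbiased, conservative paired comparison, and a secondary model may legitimately differ from the primary one. Further, SA1 (first phase only) is free of a phase effect, and SA4 (pre-COVID data) and secondary analysis (b), with its time variable, also bear on the question.

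Most of this stands as a limit on weight. The smaller shifts and milder splits are the better guide, type I inflation is not the main harm, and the phase term would not deal with delays that affect individuals differently.

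It does not remove the point. The SAP gives no reason for omitting from its primary model a term it uses for the secondary outcomes. SA1 gives up the within-person comparison, SA4 truncates by calendar date, and (b) is a trajectory model. They may expose a phase-driven result, but none corrects the primary test.

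**Conclusion.** The concern holds and should be fixed. Model (1) omits phase, and order cannot stand in for it. The consequence is nil if HbA1c does not shift between phases. For a shift of 0.25 to 0.5 SD it is a loss of roughly 2 to 8 power points with equal completer arms (81.8% to 79.4% or 74.1%). With unequal arms there is a bias of 9% to 21% of the shift over the splits from 18/15 to 20/13, in a direction set by the sign of the shift and by which arm is larger. These sizes rest on the assumed shift, effect, splits and completer number of 33; the SAP supplies none of them. The omission itself, and the algebra of bias and SE, do not depend on those assumptions. This is a weakness of the primary analysis, not evidence that its result is wrong.

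**What to change.** Add a fixed effect for phase (I versus II) to model (1), in both text and equation; keep Order and Diabetes; and test Diet in that model. Carry the term into the weight-adjusted and adherence-adjusted sensitivity models and into the diet-by-diabetes interaction model. State that a phase term does not remove carryover that differs by diet.

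The cost is one term and one within-person degree of freedom, with no new data. If there is no shift, the SE is unchanged at 20/20 and rises by a factor of 1.023 at 20/13, where LRT power goes from 73.3% to 72.4%. The term does not cure the slight small-sample excess of the chi-square LRT (5.8% to 6.0% with phase against a nominal 5%), which is a separate matter.

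### The diet tests use a likelihood-ratio test at 0.05 in at most 40 complete pairs, with no reference distribution or small-sample correction named; the default chi-square cut-off gives a true size of about 5.5 to 6%.

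*SAP*

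**What the plan says.** Under Primary Analysis, HbA1c percent change is modelled with a linear mixed model that compares the diets "while adjusting for fixed effects: order (e.g. study arm), pre-diabetes vs. diabetes status, and a random effect for each participant, i". Model (1) has no phase term. For the diet coefficient, "we will use a two-sided likelihood ratio test to test for no difference between diet types".

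The last paragraph of that section covers the secondary outcomes. It lists lipids, insulin, glucose, blood pressure and short-chain fatty acids, in models "adjusting for order, phase, pre-diabetes vs. diabetes status, and repeated measures", and repeats the method: "A two-sided likelihood ratio test will be used to assess no difference between diet types".

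The level is common to all: "A significance level of 0.05 is set for all analyses".

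On sample size, Study Design says "Forty participants are planned to be randomized between the two arms". Primary Analysis adds "The primary analysis will be a complete case analysis" and "patients who did not complete both phases (i.e. crossover) will be excluded". If the planned number is met, 40 complete pairs is therefore the ceiling.

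The SAP does not state which distribution the likelihood-ratio statistic is referred to, whether fitting is by maximum likelihood (ML) or REML, or any small-sample adjustment. It plans no confidence interval for the diet effect.

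**The concern.** A likelihood-ratio test of a fixed effect needs ML fits, because REML likelihoods are not comparable between models with different fixed effects. ML variance estimates take no account of the degrees of freedom spent on the fixed effects, and the usual chi-square reference is only a large-sample approximation. In a crossover with at most 40 pairs, both features push the test towards rejecting too often. At stake is whether the 0.05 level holds for the diet tests, and whether a borderline diet difference would be declared that a t test on the same data would not support.

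**Working it through.** **Inputs.** From the SAP: level 0.05, a two-sided test of one diet coefficient, at most 40 complete pairs, no phase term in model (1), phase included in the secondary models. Assumed, because the SAP does not say: chi-square reference on 1 df, ML fitting, normal errors, one value per phase per participant, and completer numbers below 40.

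**The stated level.** The 0.05 is reproduced only as a large-sample limit: the chi-square(1) cut-off is 3.8415 = 1.96².

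**Finite samples.** With complete pairs, diet is a purely within-participant contrast. When the estimated participant variance is above zero, the ML statistic is

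LR = n × ln(1 + t²/df),

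where t is the within-participant t statistic, df = n − 1 for model (1) and df = n − 2 with phase. Rejecting when LR > 3.8415 is the same as rejecting when

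|t| > √(df × (exp(3.8415/n) − 1)),

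and the true size is 2 × P(T_df > that value).

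At n = 40, exp(3.8415/40) − 1 = 0.1008. Model (1): √(39 × 0.1008) = 1.983, against an exact 5% value of 2.023. With phase: √(38 × 0.1008) = 1.957, against 2.024.

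| Complete pairs | Size, model (1), no period effect | Size, with phase |
|---|---|---|
| 40 | 5.45% | 5.77% |
| 33 (assumed) | 5.55% | 5.95% |
| 30 (assumed) | 5.60% | 6.05% |
| 20 (assumed) | 5.93% | 6.66% |

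**Simulation.** One million null trials per setting, including fits in which the participant variance is estimated as zero, agree at within-participant correlations of 0.5 to 0.7 (n = 40: 5.4% and 5.7%). At correlation 0 the size is higher (n = 40: 6.4% and 6.6%).

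**Interaction.** Adding the diet-by-diabetes term to model (1), as planned under Secondary Analysis, leaves n − 2 within-participant df. Its size is therefore close to the with-phase column, again with no period effect.

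**Where a conclusion changes.** Put the exact critical t into the LR formula. Model (1), n = 40: 40 × ln(1 + 2.0227²/39) = 3.990, a chi-square p of 0.0458. With phase: 40 × ln(1 + 2.0244²/38) = 4.097, p = 0.0430. Only likelihood-ratio p-values between these and 0.05 would be called significant when the t test is not. At an assumed 33 pairs the lower ends are 0.0449 and 0.0415.

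**Period effect in model (1).** If a period effect exists and the sequences are balanced, it cancels from the diet estimate but inflates the residual variance. The same rejection rule was simulated with 400,000 null trials per setting. The period effect shifts the within-person diet difference up in one sequence and down in the other, and is measured in SDs of that difference.

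| Sequence sizes | 0.2 SD | 0.3 SD | 0.5 SD |
|---|---|---|---|
| 20/20 | 5.0% | 4.5% | 3.2% |
| 17/16 (assumed) | 5.1% | 4.6% | 3.3% |
| 19/14 (assumed) | 5.4% | 5.3% | 4.9% |

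**Interval, if one were obtained by inverting the test.** The ratio of critical values is 0.980 (model 1) and 0.967 (with phase) at n = 40, and 0.976 and 0.959 at n = 33. Such an interval would be 2 to 4% too short.

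**The case against.** The strongest reply is that a prespecified likelihood-ratio test of a fixed effect in a mixed model is standard, that the excess is about half a percentage point for the primary test, and that the SAP never commits to a chi-square reference. A Bartlett correction, a parametric bootstrap or a permutation reference would also be a likelihood-ratio test. The last point is right as far as it goes: the SAP leaves the reference open. But chi-square is what software returns by default, and nothing in the SAP would lead an analyst elsewhere.

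It can also be said that the direction of the error in the primary test is not settled, because model (1) omits phase. This stands. With balanced sequences, a modest period effect offsets the excess or makes the test conservative. It does not rescue the listed secondary models, which include phase.

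The t test is exact only under normal errors, and the outcomes are percent changes in variables such as triglycerides and insulin. That is fair, but the likelihood-ratio figures rest on the same assumption.

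A reader might infer more than the document supports:

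- **The level is exceeded for the primary test at every attainable sample size.** This holds only without a period effect.
- **Every secondary outcome is affected.** Weight and alpha diversity are secondary outcomes in Study Design, but the model paragraph does not list them. If several visits per phase enter those models through their repeated-measures adjustment, the n − 2 formula does not apply as it stands.
- **The reported intervals will be too short.** None is planned.
- **The sensitivity analyses run at 6 to 7%.** The formula gives 6.3% at 15 pairs and 7.0% at 10 for model (1), and 7.3% at 15 with phase. The SAP gives no such subset sizes and does not say that SA4 or SA5 use this test. SA1 is a two-sample comparison.

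**Conclusion.** The point holds, and it is small. With the default chi-square reference the likelihood-ratio test misses the SAP's own 0.05 by about 0.5 percentage points for model (1) when there is no period effect, and by about 0.8 to 1 point for the listed secondary models, at 33 to 40 complete pairs. The interaction test is affected to a similar degree. These figures rest on ML fitting, normal errors, one value per phase and a within-participant correlation that is not low; completer numbers below 40 are assumed. The excess would be larger with clearly fewer than 30 completers or a low correlation, and for model (1) it disappears or reverses under a modest period effect with balanced sequences. Only results close to 0.05 could change. The change is worth making because a better-calibrated test of the same coefficient in the same model is available at almost no cost.

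**What to change.** Replace the two likelihood-ratio sentences under Primary Analysis with a statement that the same mixed models are fitted by REML and that diet is tested with a t or F test using Kenward-Roger (or Satterthwaite) degrees of freedom. State that the same applies to the diet-by-diabetes interaction under Secondary Analysis. If a 95% interval for the diet effect is reported, make it the matching t-based one. With complete pairs this is the within-participant t test, with size 5% under normal errors (for model (1), again with no period effect). If the likelihood-ratio test is kept, name its reference distribution and its small-sample correction.

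The cost is one SAP sentence and a software option. P-values become slightly less favourable: at 40 pairs the critical |t| rises from 1.983 to 2.023 for model (1) and from 1.957 to 2.024 with phase. The change of test does not deal with a period effect omitted from model (1); where that already makes the test conservative, the larger critical value makes it slightly more so.

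### The primary HbA1c analysis drops randomised participants who did not cross over, and no planned analysis is defined to estimate the diet contrast from everyone with an on-diet HbA1c

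*SAP*

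**What the plan says.** Study Design sets the size: "Forty participants are planned to be randomized between the two arms". Primary Analysis specifies model (1), a linear mixed model for relative HbA1c change with order, diabetes status and diet as fixed effects "and a random effect for each participant". It is tested by a two-sided likelihood ratio test, and "A significance level of 0.05 is set for all analyses".

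The same section fixes the analysis set: "The primary analysis will include participants with baseline blood draws, and at least one blood draw in each phase (including crossing over"). It calls the analysis complete-case and adds that "patients who did not complete both phases (i.e. crossover) will be excluded". Both rules are worded for the primary analysis.

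The sensitivity analyses in that section change covariates only: large baseline imbalances, weight and adherence. SA1 to SA5, under Sensitivity Analysis, are introduced for COVID-19 delays: "Potential impact of delays are unclear; subsequently, we will perform a number of sensitivity analyses". For SA1, "we will consider only the first phase (12 weeks) of each group and compare differences (two-sample"). SA2 to SA5 change which measurements or which part of the data are used. In secondary analysis (b), "we will use all time points in a model similar to (1) but with a time variable".

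**The concern.** Someone with a valid Phase I HbA1c who never starts Phase II is removed because of an event after randomisation. The SAP expects such losses, since it writes a rule for them. It also treats differences between the diets in adherence and satisfaction as open questions, so loss that depends on the first diet cannot be ruled out.

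Suppose people who respond poorly to their first diet tend to leave, and do so more on one diet than on the other. The remaining pairs then flatter that diet. The discarded Phase I values are the data that would reveal this, and the chosen model can use them. What is at stake is whether readers can see that the primary result does not depend on the exclusion.

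**Working it through.** **1. What each planned analysis covers**

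| Analysis | What it changes | Does it restore participants who did not cross over? |
|---|---|---|
| Imbalance, weight and adherence adjustments | covariates | not stated |
| SA1 | Phase I only, two-sample | yes on a plain reading; not stated |
| SA2, SA3 | which end-of-phase value is used | not stated |
| SA4 | data before 16 March 2020 | not stated |
| SA5 | data from the grocery-delivery period | not stated |
| Secondary (b) | all time points, with a time term | not stated |

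None is defined as the diet contrast on all randomised participants with an on-diet HbA1c.

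**2. Inputs**

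From the SAP: N = 40, model (1), two-sided 0.05. The SAP gives no dropout rate, mechanism, SD or correlation, so there is no figure to reproduce and the rest is assumed: 20 per sequence, no true diet effect, within-person SD 1, correlation ρ = 0.5 (total variance 1/(1 - 0.5) = 2), and 10/20/30% dropout before Phase II. Bias is for WFKD minus Med-Plus, so a negative value favours WFKD.

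**3. Bias by formula, response-driven loss in the WFKD-first sequence only**

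Let selective loss shift the mean Phase I value of those remaining in that sequence by d. Their Phase II mean shifts by ρd, so their mean pair difference shifts by (1 - ρ)d. The other sequence is unaffected. With equal numbers:

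- completer bias = (1 - ρ)d/2
- bias of SA1 if limited to those who crossed over = d
- ratio of the second to the first = 2/(1 - ρ): 2.9 at ρ = 0.3, 4 at 0.5, 6.7 at 0.7

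In simulation d = -0.17/-0.31/-0.46. Then 0.25 × d = -0.043/-0.078/-0.115, which agrees with the simulated completer bias below.

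**4. Simulation**

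Model (1) was fitted by maximum likelihood with estimated variances and tested at 3.84. Dropout was logistic with slope 1.5 per SD in WFKD-first, and random at the same rate in the other sequence. There were 20,000 trials per main scenario (Monte Carlo SE 0.002 for model bias, about 0.16 points for rejection).

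| Dropout before Phase II | 10% | 20% | 30% |
|---|---|---|---|
| *Loss driven by Phase I response, one sequence* | | | |
| Completer bias | -0.04 | -0.08 | -0.12 |
| as a fraction of its SE | 0.19 | 0.31 | 0.44 |
| Completer null rejection | 5.6% | 6.6% | 8.0% |
| same test under random dropout | 5.4% | 5.6% | 5.9% |
| All-available bias | within 0.003 of 0 | within 0.003 of 0 | within 0.003 of 0 |
| *Loss driven by the participant effect, one sequence* | | | |
| Completer bias | about 0 | about 0 | about 0 |
| All-available bias | +0.03 | +0.06 | +0.08 |

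SA1 on everyone with Phase I data is unbiased. With random dropout, or the same dependence in both sequences, both model fits are within 0.004 of zero.

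**5. Precision**

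At 20% dropout, completers have SE √(2/32) = 0.250 and the all-available fit has 0.245. SA1 on all 40 has SE √(2 × (1/20 + 1/20)) = 0.447 (simulated 0.446), and 0.446/0.245 = 1.8. That ratio depends on ρ. With 8 of 40 not crossing over, in total-SD units, it is 0.316/0.202 = 1.6 at ρ = 0.3 and 0.316/0.135 = 2.3 at ρ = 0.7.

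**6. Range**

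- Response-driven completer bias is -0.05/-0.09/-0.13 at ρ = 0.3, -0.03/-0.06/-0.09 at ρ = 0.7, and -0.02/-0.05/-0.07 with half the slope (0.75).
- Adding a phase term leaves it at -0.045/-0.078/-0.115.
- A harsher rule, in which exactly the 4 worst of 20 WFKD-first responders leave and nobody else does, gives -0.074 total SD at ρ = 0.5. Against SE √(2 × 0.5/36) = 0.167 that is 0.44 SE. With the 6 worst it is 0.097/√(1/34) = 0.57 SE.

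**7. Clinical scale**

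Assume a within-person SD of 3 to 6 points of relative change and HbA1c of 6 to 7%. The main-scenario bias then runs from 0.04 × 0.03 × 6 = 0.007 to 0.12 × 0.06 × 7 = 0.05, or about 0.01 to 0.05 HbA1c units.

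**The case against.** The strongest reply is that the plan is open and coherent. Completer pairs are a usual choice in a crossover trial, the rule is stated, and the exclusion is worded for the primary analysis only. SA1 needs no Phase II data, so on its plain wording it already keeps everyone with a Phase I value and is immune to the loss described. Secondary (b) carries a diet term and no stated exclusion, and SA4 subsets data rather than people. The harm is small: at 10% dropout, selective loss adds 0.2 points to the rejection rate, which simulation error alone could produce. The proposed addition is the biased one when loss follows the participant effect.

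Most of this stands. It answers three stronger readings that a reader might infer:

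- *SA1 also drops those who did not cross over.* The SAP does not say so, and the plain reading is the opposite.
- *The primary estimate is biased.* That needs a dropout mechanism on which the SAP is silent.
- *Completers should be replaced as the primary set.* Neither fit is better under every mechanism.

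One part remains. SA1 discards all Phase II data and is too imprecise to expose a bias of this size, and neither SA4 nor (b) is defined as a check on the primary contrast. A fit that uses data already collected would fill that gap.

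**Conclusion.** The point holds as an inexpensive improvement, not as an error that invalidates the primary analysis. The exclusion is explicit, and no planned analysis is defined to estimate the diet contrast from all randomised participants with an on-diet HbA1c.

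The possible harm is conditional: loss must depend on Phase I response and differ by sequence. In the logistic scenarios the completer bias stays under half a standard error, and selective loss adds about 0.2, 1.0 and 2.1 points to the null rejection rate at 10%, 20% and 30% dropout. Only an extreme cut-off rule takes the bias somewhat beyond half a standard error. The gain in precision from adding the excluded participants is slight. All sizes rest on the assumed dropout, correlation and SD.

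The unstated populations of SA1, SA4 and (b) are a matter of clarification. It is worth a sentence because, under response-driven loss, an SA1 limited to those who crossed over would carry about 3 to 7 times the bias of the primary analysis for correlations of 0.3 to 0.7.

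**What to change.** Keep the completer analysis as primary. Add one named sensitivity analysis that fits the same mixed model by maximum likelihood to all randomised participants with a baseline and at least one on-diet HbA1c in either phase, in assigned order. Report it beside the primary result, with dropout by sequence and by Phase I HbA1c change.

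As a minor clarification, state that SA1 includes all participants with Phase I data whether or not they crossed over, and state the populations of SA4 and secondary analysis (b).

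The cost is a few lines of SAP text and one extra model run. The downside is that the added fit relies on missing-at-random. It is itself biased, by up to about +0.08 within-person SD in the scenarios above, if loss follows the unobserved participant effect in one sequence, where the completer fit is not. Both results should therefore be shown, and a gap between them read against the dropout pattern.
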